4.6 Subgroup Analyses and Effect of Baseline Factors

4.6.1 Subgroup Descriptive Statistics

The consistency of the treatment effect for the co-primary and first secondary endpoints will be assessed descriptively, for both the AAS and BAS, using summary statistics by categories of the following:

- Age category (<65 vs. ≥ 65 years)
- Site
- Ocular Adverse Events (study eyes with vs. study eyes without)
- Preoperative Ocular Pathology (study eyes with vs. study eyes without)

To examine inter-site variation in outcomes, forest plots of co-primary and first secondary endpoints will be produced by plotting the difference in means and corresponding 95% (two-sided) confidence intervals at each site (and by pseudo-site described in Section 2).

4.6.2 Propensity Score Analysis

A propensity score is the conditional probability of being in the treatment group based on individual covariates at baseline. In a non-randomized study, baseline differences in covariates, amongst groups, may lead to a biased estimate of the treatment effect. To account for these differences the following two-step methodology outlined in (D'Agostino, 1998^[4]) will be employed.

Step 1: Fit a logistic regression model with the following baseline covariates to estimate the probability of being in the treatment group and creating the propensity score weights.

- 1) Age, continuous
- 2) Gender
- 3) Site
- 4) Baseline photopic best-corrected distance visual acuity

The SAS pseudo code for this step is provided below:

```
proc logistic data=Visual_acuity;
  where OPERATIVE_EYE = 'First' AND VISIT='VISIT4A';
  class SEX SITE LENS_MODEL;
  model LENS_MODEL (event='TFNT00') = AGE SEX SITE
    BCDVA_B /link=logit rsquare;
  output out=ps_set pred=ps;
run;

data ps_set;
  set ps_set;
  if TRT='TFNT00' then ps_weight=1/ps;
  else ps_weight=1/(1-ps);
run;
```

Step 2: Fit a propensity score-weighted linear regression model, using the GLM procedure.

```
proc glm data=ps_set;
  where OPERATIVE_EYE = 'First' AND VISIT='VISIT4A';
  class LENS_MODEL;
  model VA = LENS_MODEL /solution;
  weight ps_weight;
  lsmeans LENS_MODEL /pdiff cl;
  estimate 'Trt_eff' LENS_MODEL 1 -1;
run;
```

The estimated treatment effect from the above model will be compared to the estimated effect from the primary analysis mixed effects model. Meaningful differences will be investigated with additional exploratory analyses.

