7.2 Clinical Trial Design

This study is a prospective, multicenter, non-randomized, vision assessor-masked, parallel-group confirmatory trial. It compares an investigational trifocal IOL and a commercially available monofocal IOL. [REDACTED]

[REDACTED] (Note that neither laser nor any other types of refractive procedures are allowed at any time in the clinical trial.) The study will include adults (≥ 22 years of age) who require bilateral cataract extraction. Potential subjects will be screened for enrollment into the trial. Those qualifying will attend a total of 10 visits (7 visits occur postoperatively) over a 7 month period.

This study is not randomized. Because the test and control IOL designs offer different risks and benefits, trial subjects will be allowed to select the lens model that best fits his or her lifestyle. After careful consideration and consultation, the subject will be allowed at the time of consent to select the lens model that will be bilaterally implanted. Post consent, the electronic data capture (EDC) system will assign the subject number. To mitigate the risk of bias, the assessor

will be masked for all vision assessments. The subject will be provided with his/her permanent implant card at the time of implant.

Standard clinical trial methods that minimize bias in multicenter studies will be used such as standardized test procedures, common investigator training, and common inclusion/exclusion criteria.

No interim analysis of the data will be conducted. Final data analysis will be conducted at study completion.

An overview of the study design is depicted in Table 7-1.

Table 7-1 **Study Design**

Time From Implantation	First Eye	Second Eye
-30 to 0 days pre-operatively	Visit 0 (monocular [First and Second eye] and binocular)	
Operative (IOL implantation)	Visit 00	Visit 00A*
1 - 2 days post-operatively	Visit 1 (monocular)	Visit 1A (monocular)
7 - 14 days post-operatively	Visit 2 (monocular)	Visit 2A (monocular)
30 - 60 days post-operatively	Visit 3 (monocular)	Visit 3A (monocular)
120 - 180 days post-operatively (after Second eye implantation)	Visit 4A" (monocular [First and Second eye] and binocular)	

*NOTE: IOL implantation in the second eye is intended to occur between 7 and 30 days after IOL implantation in the first eye.

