11.4 Assessor Masking

The assessor associated with vision testing will be masked in this study. Site personnel performing [REDACTED], all VA assessments [REDACTED] and all contrast sensitivity assessments will remain masked with regard to treatment assignment until after the final database lock (Visit 4A).

Note: Any unmasking of the masked assessor must be reported to Alcon.

Masked study personnel must avoid seeking information that may compromise masking. Unmasked study personnel must not disseminate information that is potentially unmasking to any masked personnel. A list of unmasked individuals can be found in Table 11-1 below.

Table 11-1 Unmasked Individuals

Unmasked Individual	Extent of Unmasking	Rationale
Subject	Unmasked to IP selection	The test and control IOL designs offer different risks and benefits. The subject will select the lens model that best fits his or her lifestyle.
Investigator	Unmasked to IP selection	Investigator will be advising the subject on the different risks and benefits of the IP to help the subject select the lens model that best fits his or her lifestyle.
Site Personnel (not completing assessments noted in section 11.4)	Unmasked to IP selection	Site personnel involved with operative visits and data entry into EDC
Monitor	Unmasked to IP selection	Monitor will complete IP accountability and monitoring responsibilities

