2.1 Effectiveness Analysis Sets

The All-Implanted Analysis Set (AAS) includes all eyes with successful IOL implantation with at least one post-operative visit and will be the primary analysis set for all effectiveness analyses except [REDACTED] [REDACTED]

The Best-Case Analysis Set (BAS) will be the primary analysis set for [REDACTED] and contrast sensitivity, and includes all eyes successfully implanted that had:

- at least 1 post-operative visit;
- no preoperative ocular pathology;
- no macular degeneration detected at any time; and
- no major protocol deviations.

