2.3 Pharmacokinetic Analysis Set

Not Applicable.

3 Subject Characteristics and Study Conduct Summaries

Subject characteristics and study conduct summaries include tables and listings such as an accountability table (similar to Table A.1 in IS EN ISO 11979-7:2014), demographics (including age, gender, race, ethnicity) and baseline characteristics (including axial length, anterior chamber depth, lens thickness) tables, summary of screen failures by reason, and listing of subjects excluded from analysis sets including reasons. All descriptive summary statistics will be displayed with n and % for categorical data, and with mean, median, standard deviation, number of subjects/eyes, minimum, and maximum for continuous data. Tables will be presented by IOL group and overall.

Subject characteristics and study conduct summaries will be presented for the all-implanted analysis set, the best-case analysis set and the safety analysis set.

4 Effectiveness Analysis Strategy

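### The SAP's only visible covariate-adjusted analysis of self-selection, the propensity model in 4.6.2, leaves out preoperative ocular pathology

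*SAP*

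**What the plan says.** **Allocation.** Protocol 7.2 states that "trial subjects will be allowed to select the lens model that best fits his or her lifestyle". Protocol Table 11-1 lists the investigator as unmasked and adds: "Investigator will be advising the subject on the different risks and benefits of the IP".

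**Primary analysis.** SAP 4.3.1 fits lens model as the only fixed effect, with random site terms and no baseline covariate. The All-Implanted set (AAS) is the primary set for effectiveness (SAP 2.1), and its definition has no pathology exclusion.

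**Propensity analysis.** SAP 4.6.2 acknowledges that baseline differences can bias the lens comparison in a non-randomised study. Step 1 is: "Fit a logistic regression model with the following baseline covariates to estimate the probability of being in the treatment group". Four covariates are listed, and the code agrees: "model LENS_MODEL (event='TFNT00') = AGE SEX SITE", with the fourth being "Baseline photopic best-corrected distance visual acuity". Step 2 weights a linear model of visual acuity. The result is compared informally with the primary estimate.

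**Where pathology appears.** It is a factor for descriptive summaries of the co-primary and first secondary endpoints in SAP 4.6.1: "Preoperative Ocular Pathology (study eyes with vs. study eyes without". It also defines the Best-Case set (BAS) in SAP 2.1, which requires "no preoperative ocular pathology".

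**The concern.** A weighted analysis removes confounding only by the covariates in its model or by factors closely tied to them. Here a factor that the SAP already derives, and treats as relevant to the same endpoints, is left out of the one visible analysis meant to adjust for self-selection. Baseline BCDVA does little to replace it, because preoperative acuity is dominated by the cataract that surgery removes.

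The stake is mainly the BCDVA non-inferiority result. If eyes with pathology were chosen or advised toward the monofocal lens, the control mean would worsen and TFNT00 would look better against the 0.10 logMAR margin. A weighted estimate that does not balance pathology could then agree with the primary estimate and be read as reassurance. Selection in the other direction would bias against TFNT00. The documents do not say which way, if either, pathology influenced the choice.

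**Working it through.** **Inputs from the documents.** Margin 0.10 logMAR (SAP 4.2.1); SD 0.18 logMAR, expected BCDVA difference 0, 113 completers per arm (SAP 7); one-sided 5% for non-inferiority and 2.5% for superiority (SAP 4.3).

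**Inputs not in the documents (assumptions).** Excess of pathology in the control arm: 10 to 30 percentage points. Mean cost of pathology in month-6 BCDVA: 0.05 to 0.10 logMAR.

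**1. The plan's own figures.** SE = 0.18 × √(2/113) = 0.0239. Non-inferiority power = Φ(0.10/0.0239 − 1.645) = 99.4%, stated as 99%. Superiority power for a 0.1 difference = Φ(0.10/0.0239 − 1.960) = 98.7%, stated as 98%. Both reproduce.

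**2. Room in the test.** One-sided 95% half-width = 1.645 × 0.0239 = 0.039. The largest observed difference that passes is 0.10 − 0.039 = 0.061 logMAR.

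**3. Size of the bias.** Bias = imbalance × cost. If the true difference equals the margin, the chance of a false pass is Φ(bias/SE − 1.645).

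| Imbalance | Cost (logMAR) | Bias (logMAR) | Share of margin | False pass at the margin |
|---|---|---|---|---|
| 0 | – | 0 | 0% | 5% |
| 10 points | 0.05 | 0.005 | 5% | 7.5% |
| 10 points | 0.10 | 0.010 | 10% | 11% |
| 20 points | 0.05 | 0.010 | 10% | 11% |
| 20 points | 0.10 | 0.020 | 20% | 21% |
| 30 points | 0.05 | 0.015 | 15% | 15% |
| 30 points | 0.10 | 0.030 | 30% | 35% |

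**4. Does weighting on baseline BCDVA remove it?** Simulation: 226 subjects, 1,500 runs per setting, average pathology prevalence 20%, cost 0.10 logMAR, SD 0.18 for both baseline and month-6 BCDVA. Pathology worsened baseline BCDVA by either 0 or 0.10 logMAR. Age, sex and site were not simulated. Mean bias with the 0.10 baseline shift, where negative favours TFNT00:

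| Imbalance | Unadjusted | Weighted on baseline BCDVA | Weighted, pathology added | No-pathology eyes only |
|---|---|---|---|---|
| 10 points | −0.010 | −0.010 | 0.000 | 0.000 |
| 20 points | −0.020 | −0.020 | 0.000 | −0.001 |
| 30 points | −0.030 | −0.029 | 0.000 | 0.000 |

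Even when pathology shifts baseline acuity by as much as it shifts the outcome, weighting on baseline BCDVA removes almost none of the bias. Adding the pathology term removes it. With no baseline shift, all biases are within about 0.002 logMAR of these.

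A few fits with the pathology term did not converge. On re-running, this occurred only at the 30-point imbalance, in runs where no test eye had pathology. Prevalence in the test arm is then 5%, so the chance of this is 0.95^113 = 0.003 per run.

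**The case against.** **The SAP has other views of pathology.** SAP 4.6.1 summarises the co-primaries with and without pathology, and the BAS drops those eyes. The simulation shows that the lens difference among no-pathology eyes is free of this bias. This stands: a reader might infer that 4.6.2 is the only check on self-selection, or that confounding by pathology could not be detected, and the SAP supports neither. Parts of the effectiveness sections are also redacted, so no claim can be made about what they contain. The limits of these views are that 4.6.1 is descriptive and specifies intervals for lens differences by site only. The BAS also removes macular degeneration and major deviations, so AAS against BAS does not isolate pathology. Neither yields an adjusted lens effect in the set that decides the trial.

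**Pathology may not drive the choice.** A reader might infer that it is the likeliest confounder. The documents name lifestyle and the lenses' risks and benefits, and they do not rank confounders. This stands.

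**Entry criteria limit what is left.** Protocol 10 rules out pathology that could confound outcomes, 10.1 requires projected BCDVA of 0.2 logMAR or better, and 10.2 lists many exclusions, including disease expected to leave BCDVA worse than 0.30. This largely stands, and it argues against larger figures. A 20-point imbalance with a 0.20 logMAR cost would give 0.04 logMAR, about the whole half-width. If unaffected eyes average 0.0 logMAR (an assumption), that cost puts the average pathology eye at the projected-acuity limit, so this is an extreme case. Some pathology must still be expected, since the SAP plans a subgroup for it.

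**More covariates could do harm.** With about 12 sites, Step 1 already has about 14 slopes (11 for site, plus age, sex and BCDVA), or 113/14 ≈ 8 subjects per slope in an arm. This argues against also adding the collected biometry or the questionnaire answers. Nothing in the documents links IOLSAT or QUVID answers to best-corrected acuity. The schedule row that places them at Visit 0 also does not match the visit procedures, although much of the Visit 0 list is redacted. One binary term adds little to this burden.

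**Conclusion.** The omission is real and worth correcting. The only covariate-adjusted analysis of self-selection that can be seen in the SAP does not balance a baseline factor that the SAP itself uses for the same endpoints and that the AAS retains. Under the assumed ranges, the bias toward non-inferiority is 0.005 to 0.030 logMAR. That is 13% to 76% of the half-width (0.005/0.0394 and 0.030/0.0394) and 5% to 30% of the margin. These sizes rest wholly on assumed imbalance and effect, with pathology more frequent in the control arm and not explained by the other covariates.

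No stated figure in either document is wrong. The propensity analysis is supportive and decides no hypothesis, so the point concerns how far its agreement with the primary result can be trusted. It does not show that the primary result is biased.

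**What to change.** In SAP 4.6.2:

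- Add first-eye preoperative ocular pathology (yes/no) to the Step 1 list and to the model statement.
- Report standardised differences between lens groups, before and after weighting, for every covariate in the model.
- Compare the re-weighted BCDVA, DCNVA and DCIVA effects with the primary estimates.

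The variable is already needed for SAP 4.6.1 and for the BAS, so nothing new is collected. The cost is a line of text, one model term and a balance table, with slightly more variable weights. If one arm has no pathology eyes the term cannot be estimated; the SAP could say that the difference among no-pathology eyes is reported instead. The primary model, the tests and the sample size do not change.

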All expected differences for tests of superiority favor the test lens. Estimates for VA endpoints reported

in logMAR.

Adverse Events: For any event where a zero incidence is observed in 113 first-operative eyes in the AcrySof IQ PanOptix IOL test group, the upper exact binomial 95% confidence limit is less than 3%. Thus, with 95% confidence, the true adverse event rate is less than 3%.

8 References

1. Littell, R. C., Stroup, W. W., Milliken, G. A., Wolfinger, R. D., & Schabenberger, O. (2006). *SAS for mixed models*. SAS institute. (Section A1.6.1)
3. Ratitch, B. and O'Kelly, M. Implementation of Pattern-Mixture Models Using Standard SAS/STAT Procedures. *Proceedings of PharmaSUG 2011 (Pharmaceutical Industry SAS Users Group)*, SP04, Nashville (2011).
4. D'Agostino, R.B. 1998. "Tutorial on Biostatistics: Propensity Score Methods for Bias Reduction in the comparison of a treatment to a non-randomized control group". *Statistics in Medicine* 17, 2265-2281

9 Revision History

Changes in the first revision include clarifying confidence limits for the hypothesis tests and multiplicity strategy to match the protocol, detailing which personnel will be masked, adding a sensitivity analysis for primary effectiveness, revising the categories for visual acuity, adding a propensity score analysis to account for baseline differences in covariates, updating the contrast sensitivity analysis, updating the sample size justification section to reflect modified Type I error rates, and minor corrections throughout for consistency and typographical errors.

Change in the second revision includes adding categorical statistics of subjects who meet visual acuity thresholds at all distances.

Date/Time (mm/dd/yyyy GMT):	Signed by:	Justification:
09/14/2018 18:51:00	[REDACTED] [REDACTED]	[REDACTED]
09/17/2018 19:51:29	[REDACTED] [REDACTED]	[REDACTED]
09/18/2018 16:56:30	[REDACTED] [REDACTED]	[REDACTED]
09/26/2018 15:22:27	[REDACTED] [REDACTED]	[REDACTED]

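### SAP 4.6.2: the weight step tests TRT where the other code uses LENS_MODEL, and PROC GLM's SE, p-value and CI are not valid for inverse-probability weights

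*SAP*

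**What the plan says.** Lens assignment is by choice: Protocol 7.2 states that "trial subjects will be allowed to select the lens model that best fits his or her lifestyle". SAP Section 9 records that the first revision made several changes, among them "adding a propensity score analysis to account for baseline differences in covariates".

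SAP 4.6.2 sets this out in printed SAS pseudo code:

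- **Propensity model.** A logistic regression with lens as the response: "model LENS_MODEL (event='TFNT00') = AGE SEX SITE", plus baseline distance acuity.
- **Weights.** A data step on the logistic output: "if TRT='TFNT00' then ps_weight=1/ps". The fallback line begins "else ps_weight=1/(1-ps".
- **Outcome model.** "Fit a propensity score-weighted linear regression model, using the GLM procedure", with those weights in a WEIGHT statement. The output request is "lsmeans LENS_MODEL /pdiff cl", so a p-value and confidence limits will be produced. No robust or bootstrap variance is named.
- **Use.** "The estimated treatment effect from the above model will be compared to the estimated effect from the primary analysis mixed effects model". Meaningful differences are then to be explored. No test or CI criterion is attached.

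**The concern.** There are two separate defects.

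1. **Treatment variable.** The weight step tests a variable that no printed step creates. If it is not on the data set, every subject falls into the same branch whatever lens was implanted. The output would still look like an adjusted estimate. The SAP's one stated use of this analysis is to set its estimate beside the primary one, so agreement could come from the coding slip and be read as absence of confounding.

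2. **Variance.** PROC GLM treats weights as known inverse residual variances. Inverse-probability weights are not that. The reported SE ignores both the spread of the weights and the fact that the propensity score was estimated. The point estimate is unaffected, but the printed SE, p-value and CI do not measure its uncertainty.

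The primary model has only lens and site terms, so this section is the readable plan's one answer to self-selection on measured covariates.

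**Working it through.** **1. Anchor to the plan's own figures.** SAP 4.6.2 states no number. SAP Section 7 gives 113 per group, SD 0.18 and a difference or margin of 0.1. The unweighted SE is 0.18 × √(2/113) = 0.0239.
- Superiority: 0.1/0.0239 - 1.960 = 2.22, power 98.7% (plan: 98%).
- Non-inferiority: 0.1/0.0239 - 1.645 = 2.53, power 99.4% (plan: 99%).

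Both agree with the plan, so n = 226 and SD 0.18 are used below.

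**2. Variable names in the printed code.**

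| SAP section | Treatment variable |
|---|---|
| 4.3.1, both models | LENS_MODEL |
| 4.3.2.2 | LENS_MODEL |
| 4.5, control-based imputation and model on imputed data | LENS_MODEL |
| 4.5, MAR imputation and MIANALYZE | none named |
| 4.6.2, logistic model | LENS_MODEL |
| **4.6.2, weight step** | **TRT** |
| 4.6.2, GLM | LENS_MODEL |
| 5.3.1, 5.3.4 | LENS_MODEL |

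**3. What one formula for everyone does.** Let e be the propensity for TFNT00 and f the covariate distribution of all subjects. Test subjects are distributed as e·f and controls as (1-e)·f, up to constants. Correct weights (1/e and 1/(1-e)) return both arms to f. If everyone gets 1/(1-e), controls return to f but the test arm becomes f·e/(1-e), further from f than with no weighting. If everyone gets 1/e, the mirror image holds. Either way the imbalance grows.

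**4. What PROC GLM computes.** With residuals r:
- GLM variance = MSE_w × (1/Σw₁ + 1/Σw₀), where MSE_w = Σwr²/(n-2).
- Robust variance = sum over arms of Σw²r²/(Σw)².

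With correct weights each arm's weights sum to about n, so MSE_w ≈ 2σ² and the GLM SE ≈ 0.18 × √(4/226) = 0.0239. That is the unweighted SE, however uneven the weights are.

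**5. Simulation.** Neither document gives the strength of selection or how well the covariates predict acuity, so these are assumed ranges. Common to both models: 226 subjects, 12 sites, SD 0.18, true lens effect 0, and a logistic score on age, sex, site and baseline acuity.

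*Model A.* Lens logit = k(-0.8 age - 0.6 VA + 0.2 sex + 0.5 site effect), with age, VA and site effect standard normal. Outcome = 0.18[√R²(0.8 age + 0.6 VA) + √(1-R²) noise]. k = 0.4, 0.8 and 1.2 give squared CVs of the weights of 0.15 (weak), 0.37 (moderate) and 0.78 (strong).

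Bias in logMAR (negative favours the test lens), weak to moderate selection, R² 0.02 to 0.10, 4000 replicates per cell:

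| Estimate | Bias | Shift from primary |
|---|---|---|
| Primary random-site model | -0.010 to -0.039 | n/a |
| Correct weights | 0.000 (within 0.001) | +0.010 to +0.039 |
| One formula for all (either branch) | -0.011 to -0.050 | -0.001 to -0.010 |

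GLM SE divided by true SD, correct weights, 2400 replicates per cell:

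| Selection | R² 0 | 0.10 | 0.25 | 0.50 |
|---|---|---|---|---|
| Weak | 0.91 | 0.99 | 1.06 | 1.29 |
| Moderate | 0.82 | 0.86 | 0.88 | 1.01 |
| Strong | 0.69 | 0.66 | 0.71 | 0.73 |

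Coverage of nominal 95% intervals:
- GLM: 83.6% to 98.9%.
- Plain sandwich: 94.0% to 99.6%.
- Bootstrap refitting the score (400 replicates × 150 resamples, stratified by lens; R² 0, 0.10, 0.50): 93.8% to 97.0%.
- Asymptotic variance adjusted for the estimated score: 89.5% to 93.9%.

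*Model B.* Log-odds of lens choice g = 0 to 0.9 per SD of age and of baseline acuity; each covariate moves the outcome by 0, 0.3 or 0.5 SD per SD; 2000 runs per setting.
- Correct weights: bias at most 0.002 in size.
- All weighted 1/(1-e), outcome effect 0.3: -0.036, -0.069 and -0.104 at g = 0.3, 0.6 and 0.9, against -0.032, -0.056 and -0.074 unweighted.
- GLM SE about 0.024 throughout, while the true SE ran from 0.018 to 0.034. The ratio was 0.71 to 1.35 and coverage 84.9% to 99.1%. Sandwich coverage was 93.9% to 99.3%.
- Check against step 4, covariates unrelated to outcome: at g = 0.6 the effective sample size is 171, so the SE should be near 0.0239 × √(226/171) = 0.0275. Simulated: 0.0280. GLM reports 0.0239.

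**The case against.** **The code is pseudo code, and TRT may exist.** True. Several SAP listings carry a treatment variable, and the prose of 4.6.2 makes the intent clear. If the data set holds TRT with the value TFNT00, the first defect does no harm. What is certain is the mismatch; the harm is conditional. A pre-specified analysis should still not depend on a programmer noticing it.

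**The SAP compares estimates, not intervals.** Also true. The GLM weighting gives the right point estimate, no success rule uses the CI, and the primary tests do not depend on this section. But the code requests a p-value and CI, and these will be reported beside the adjusted estimate.

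**False reassurance depends on the setting.** This stands. At weak selection and R² 0.10, the one-formula estimate lies within 0.01 logMAR of the primary in about 67% of trials, against 16% with correct weights. A rerun with a simple mean difference as the primary gave about 69% v 53% at weak selection and R² 0.02, 36% v 3% at moderate selection and R² 0.10, and 21% v 3% at strong selection and R² 0.10. As selection strengthens, the enlarged bias becomes visible and could itself prompt the exploratory follow-up. It would still point the wrong way.

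**Refitting the score with site as a covariate can break down in small sites.** This is a fair practical warning, handled in the fix. It does not make the GLM variance valid.

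**Conclusion.** Both defects are present as printed. The weight step names a variable that appears nowhere else in the code. If it is undefined, the estimate retains the confounding and enlarges it: -0.011 to -0.050 logMAR against -0.010 to -0.039 for the primary model at weak to moderate selection, and more at stronger selection. The GLM SE can err either way: 0.66 to 1.29 times the true SD in one model and 0.71 to 1.35 in the other. Coverage of the nominal 95% interval ranges from about 84% to 99%.

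The sizes rest on assumed selection and prognostic strengths. The variable mismatch and the meaning of PROC GLM's WEIGHT statement do not. This is a correction to a supportive analysis, worth making because it is the plan's stated means of addressing baseline differences between self-selected groups.

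**What to change.** - In the weight step, test `LENS_MODEL='TFNT00'`, or state where TRT is defined.
- Keep the weighted point estimate and its comparison with the primary estimate.
- Take the SE, p-value and CI from a bootstrap that refits the propensity model in each resample, for example PROC CAUSALTRT with bootstrap, rather than from PROC GLM. Resample within lens group, as in the coverage figures above. State how sites with one lens only in a resample are handled; the pseudo-site rule in SAP Section 2 is one option.
- A plain sandwich variance is acceptable if simplicity is preferred, but it can be conservative.

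The cost is one variable name and one procedure. The supportive interval may become wider or narrower. No new data are needed, and no primary or secondary test changes.
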